Protocol

N-3 FATTY ACID REQUIREMENTS FOR HUMAN DEVELOPMENT

**DR. [name]
DEPARTMENT OF PEDIATRICS
UNIVERSITY OF BRITISH COLUMBIA**

Study Objectives

Compare the effects on CNS maturity, language and cognitive development, growth, and essential fatty acid status as well as serum parameters in term infants following maternal supplementation during gestation. The study supplements are:

- 1) Single cell triglyceride capsules to provide about 400mg 22:6n-3 containing an orange flavor.
- 2) Soybean/corn oil as placebo capsules containing an orange flavor.

I. CNS maturity:

Compare CNS maturity and infant blood lipid 22:6n-3 with and without an increase in the maternal intake of 22:6n-3 of 400mg/day. Compare EEG maturity, ABR amplitude and latency 48-72 hr, 3 months of age, as well as looking acuity at 2, 3 and 12 months of age.

II. Language development:

Compare speech perception at 9 months and vocabulary comprehension and production at 14 and 18 months.

III. Sleep/Wake patterns:

Compare sleep/wake cycles over a 48-hour period from weeks 4 to 8, and over a 24-hour period at weeks 10, 12, 16 and 18.

IV. Cognitive and behavioral development:

Compare infant mental and physical development at 9 months and 18 months of age and behavioral development at 6, 12 and 18 months of age.

V. Growth:

Compare growth by measuring participants weight, length and head circumference at birth, then at 1,2,3,6,9, and 18 months using standardized procedures.

VI. Nutrient intake of mothers and infants:

Compare energy, fat and nutrient intake of mothers by using a food frequency questionnaire along with a weighed 3-day record at 16 and 36 week gestation. Compare nutrient intake of infants using a feeding diary every month and an infant food frequency questionnaire at 9 & 18 months of age.

VII. Lipid and fatty acid analysis:

Compare maternal blood collected at 16 and 36 weeks gestation and infant blood at 2 months for fatty acid analysis. Compare fetal cord blood and umbilical cord tissue following delivery of the infant. Compare human milk from breast-feeding mothers at 1, 2 and 3 months post-partum.

Study design

I. Description of study:

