This will be a randomized, blinded, prospective study with 2 groups; placebo group and supplemented group with 22:6n-3. Women will be enrolled and randomized by 16 weeks gestation. An initial dietary assessment will be done and blood will be collected at 16 weeks. The dietary supplementation will then commence and continue until delivery. The dietary assessment and maternal blood sample will be repeated at 36 weeks gestation. Hospital registration charts will be marked to indicate the women who are participants in this research, and will contain a copy of the informed consent. Following delivery, fetal cord blood and umbilical cord tissue will be collected. Length of gestation, newborn infant weight, length, head circumference and gender will be recorded. The mother-infant pairs will be followed for 18 months following delivery.

To account for drop-outs, approximately 200 mothers per group will be randomized in order to have 120 participants per group.

II. Primary/Secondary Endpoints

Primary: Infant CNS maturity

Secondary: language development, sleep-wake cycle and crying behavior, cognitive and behavioral development, growth (weight, length, head circumference), maternal lipid and fatty acid analysis, gestation length and incidence of prematurity.

Selection of participants

I. Study population:

Acceptable participants will be identified from the registrations for low-risk delivery at the BC Women's Hospital and through advertising. Eligible participants will be 20-40 years of age, 12-16 weeks gestation, expected to deliver a single full-term (37-42 weeks) infant.

II. Participant Exclusion Criteria

All mothers:

- Diabetes
- Cardiac disease
- Renal disease
- Tuberculosis
- HIV/AIDS
- Hepatitis
- Previous pregnancy complications
- Substance abuse

III. Randomization

Participants will be randomized to the supplements using a random number system. The supplements will be given as 2x500mg capsules of single cell triglycerides to provide about 400 mg 22:6n-3, or soybean/corn oil as a placebo. The supplements and placebo capsules will be provided in prepackaged sealed containers for dispensing and will both contain an orange flavor to assist in further blinding. The capsules will be dispensed at 16, 26 and 36 weeks. The number of capsules remaining in each vial will be recorded, and used with the number dispensed, to calculate the number taken by each subject.

Investigational Plan

Study Procedures and Observations

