Study visits will occur when the participants are at 16 and 36 weeks gestation, and at 1, 2, 3, 6, 9, 12, 14 & 18 months postpartum.

Study visit 1 (16 weeks gestation)

- Informed consent – At or prior to this visit, the participant who meets all of the applicable inclusion criteria and none of the exclusion criteria will be contacted and the study will be explained to them. Their questions will be answered to their satisfaction. After giving time for consideration, the participant will be asked to grant permission for their infant and themselves to participate in the study. If permission is granted, an informed consent form will be signed by the participant and a copy of the signed consent written informed consent form will be provided to them.
- Verify inclusion and exclusion criteria.
- Randomization.
- Dispense supplements.
- Dietary assessment (Food frequency of prior 4 weeks + weighed 3 day food record)
- Maternal blood sample.

Study days 16 – 36 weeks gestation

- Periodic phone calls to participant.
- Dispense supplements.

Study visit 2 (36 weeks gestation)

- Dietary assessment (Food frequency of prior 4 weeks + weighed 3 day food record).
- Maternal blood sample.
- Dispense supplements.

Study days 36 weeks gestation – Day of delivery

- Periodic phone calls to participant.

Day of delivery (37 – 42 weeks gestation)

- Fetal cord blood collection.
- Anthropometric measurements of newborn (body weight, body length and head circumference).
- CNS maturation measures at 48-72 hr (EEG and ABR).

Study visit 3 (1 month postpartum)

- Breast-milk collection (breast-feeding mothers).
- Anthropometric measurements of infant (body weight, body length and head circumference).
- Infant feeding diary.

Study visit 4 (2 months postpartum \pm 2 days)

- Breast-milk collection (breast-feeding mothers).
- Anthropometric measurements of infant (body weight, body length and head circumference).
- Looking acuity assessment.
- Infant feeding diary.

Study visit 5 (3 months postpartum \pm 2 days)

- Breast-milk collection (breast-feeding mothers).
- Anthropometric measurements of infant (body weight, body length and head circumference).
- CNS maturation measures (EEG and ABR).
- Looking acuity assessment.
- Infant feeding diary.

Study months 4 & 5 postpartum

- Infant feeding diary.
- Periodic phone calls to participant.

Study visit 6 (6 months postpartum \pm 2 days)

- Anthropometric measurements of infant (body weight, body length and head circumference).

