Differences in maternal plasma, RBC, fetal umbilical cord plasma and RBC and milk fatty acids between the 2 randomized groups will be determined using one way analysis of variance (ANOVA). One way ANOVA will be used to test for differences in measures of CNS maturity, looking acuity, and language development. Regression analyses will be used to determine the relation between intake (g/day & adjusted for energy intake) of selected fatty acids and the maternal and infant blood, umbilical tissue and milk 20:4n-6, 20:5n-3 and 22:6n-3. A stepwise multiple regression will be used to predict independent factors, including gender, maternal smoking and alcohol intake (as appropriate), highest level of education attained by the mother, family income, birth order, ethnic background, and maternal weight gain in pregnancy, maternal dietary

variables, and duration of breast-feeding, associated with the developmental outcomes. The measures of weight, length and head circumference will be used to plot growth curves for each infant, then an imputation procedure used to estimate weight, length, head circumference and rate of growth from birth to exactly 4, 6, 9 and 18 month for each infant.

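### Growth is to be estimated at a 4-month age that no visit measures, with no estimate set at the measured 1, 2 and 3 months and, read literally, extrapolated values for infants lost early

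*Protocol*

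**What the plan says.** Three parts of the Protocol bear on this.

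- **Study Objectives, V. Growth** sets the ages: "Compare growth by measuring participants weight, length and head circumference at birth, then at 1,2,3,6,9, and 18 months using standardized procedures".
- **Study Procedures and Observations** places postnatal visits "at 1, 2, 3, 6, 9, 12, 14 & 18 months postpartum". The entry headed "Study months 4 & 5 postpartum" lists a feeding diary and phone calls, and no body measurements. The 12- and 14-month visits list none either.
- **Statistics, Statistical analysis** begins the growth text with "The measures of weight, length and head circumference will be used to plot growth curves for each infant". It then applies "an imputation procedure used to estimate weight, length, head circumference and rate of growth from birth to exactly 4, 6, 9 and 18 month", and says that this is done for every infant. The procedure is not named. The ANOVA sentences in the same section do not mention growth.

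On losses, Study design, I. Description of study says that "approximately 200 mothers per group will be randomized in order to have 120 participants per group". Section II there lists growth among the secondary endpoints.

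**The concern.** The objective and the analysis text name different ages. An analyst following the Statistics section would produce a 4-month comparison that rests on no 4-month measurement, and nothing at 1, 2 or 3 months. Supplementation ends at delivery, so those are the postnatal measurements closest to it.

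The second issue is reach. The sentence covers every infant and sets no limit at the last age at which that infant was measured, in a trial that plans for heavy loss. An 18-month weight, length or head circumference could then be supplied for a child last seen much earlier. What is at stake is whether the 18-month comparison describes 18-month growth, or partly the curve chosen to project earlier growth forward.

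**Working it through.** **1. Ages side by side**

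| Age (months) | Objective V | Body measurements in the visit list | Estimate in Statistical analysis |
|---|---|---|---|
| Birth | yes | yes | start of growth rate |
| 1, 2, 3 | yes | yes | no |
| 4 | no | no | **yes** |
| 6, 9 | yes | yes | yes |
| 12, 14 | no | no | no |
| 18 | yes | yes | yes |

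Three of the four analysis ages are measured; 4 months is not. Of the six measured postnatal ages, three (6, 9, 18) get an estimate and three (1, 2, 3) do not. The methods paragraphs on weight, length and head circumference say one measurement per visit, which taken literally would add 12 and 14 months. Neither Objective V nor the visit list supports that, and it would not create a 4-month measurement.

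**2. How far a curve would have to reach**

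For an infant seen at 3 and 6 months, 4 months is interpolation; on a straight line, y4 = (2/3)·y3 + (1/3)·y6. For 18 months the reach is 18 minus the last measured age:

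- last measured at 9 months: 18 − 9 = 9 months
- last measured at 6 months: 18 − 6 = 12 months
- last measured at 3 months: 18 − 3 = 15 months

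**3. How many infants this could touch**

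The Protocol gives no precision or sample-size figure for growth. Its only relevant figures imply a planned loss of 1 − 120/200 = 40%. That counts mothers randomized by 16 weeks gestation. A pair lost before delivery has no infant curve, and the timing of losses is not given, so 40% is a ceiling under the plan's own figures.

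**4. Do curve-derived values shrink the standard error?**

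Simulation with no true group difference, 4,000 runs per row, t-test at 5%. Assumptions not in the Protocol: mean weight 3.4 kg at birth, 7.8 at 6 months, 8.9 at 9 and 11.0 at 18; between-infant SD 0.5 kg at birth plus 0.06 kg per month in slope; measurement SD 0.15 kg. The 4-month row uses 120 per group. The others start from 200 per group, with 40% lost at random after 9 months.

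| Value analysed | Mean estimated SE (kg) | Actual SD of the difference (kg) | Rejections |
|---|---|---|---|
| 4 months, interpolated | 0.0729 | 0.0731 | 5.1% |
| 18 months, observed infants only | 0.155 | 0.154 | 4.9% |
| 18 months, own straight line from 6 and 9 months | 0.141 | 0.141 | 5.0% |
| 18 months, own 9-month deviation carried along the mean curve | 0.104 | 0.105 | 5.0% |
| 18 months, missing filled with the group mean | 0.093 | 0.154 | 23.8% |

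The last row agrees with algebra. Filling with the mean multiplies the sample variance by 0.6 and counts 200 instead of 120, so the SE ratio is √(0.6 × 120/200) = 0.60, and 2{1 − Φ(1.96 × 0.60)} = 0.24. Only that row, where values are borrowed from other infants, understates the error.

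**5. Where bias can enter**

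On the same assumed means, a straight line from 6 and 9 months gives 8.9 + 9 × (8.9 − 7.8)/3 = 12.2 kg at 18 months, against 11.0. The overshoot of 1.2 kg cancels between groups if equal proportions are extrapolated. Otherwise it leaves a spurious difference of 1.2 kg times the difference in proportions. The simulation had equal, random loss, so it could not show this. Dropout related to growth would add a further bias, whose size cannot be given from the Protocol.

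**The case against.** The best defence is that the sentence describes age alignment. The emphasis on exact ages suggests bringing each infant to a common age, three of the four ages are visits, and where windows are stated at those visits they are only ±2 days (6 months), ±3 days (9 months) and ±5 days (18 months). Moving a value by a few days on the infant's own curve is harmless, and interpolating 4 months between 3 and 6 is a legitimate summary if labelled as such. The choice of curve, its limits for dropouts and the growth test may be in an SAP that is not shown, so their absence is no finding. All of that stands. It does not reconcile the ages: an SAP can follow Objective V or the Statistics section on the list of ages, but those two lists differ in the Protocol itself.

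Three stronger readings are tempting, and the document does not support them.

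- **Standard errors are too small.** A reader might reason that counting 200 instead of 120 shrinks the SE to √(120/200) = 0.77 of its true size, so that a 5% test rejects 2{1 − Φ(1.96 × 0.77)} ≈ 13% of the time. This does not follow. One value per infant from that infant's own data is a summary measure, and its noise enters the between-infant variance that the test uses. Even if 80 of 200 values per group are independent pure noise, rejections stay near 5%. Inflation needs borrowing across infants, which the Protocol does not describe.
- **Attrition is hidden.** The Protocol does not say outright that infants who have left receive later values, and its Final evaluation form records completion, the reason for withdrawal and the last visit date.
- **The early comparisons are dropped.** Objective V still commits to them, and the early measurements feed each curve. The analysis text sets no estimate there; it does not cancel them.

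**Conclusion.** The concern holds in limited form. The growth ages in the Statistics section conflict with Objective V and the visit schedule: one analysis age is unmeasured, and three measured ages have no estimate. This rests on the text alone.

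The extrapolation point rests on reading the reference to every infant literally. On that reading, infants lost before 18 months would carry values projected nine months or more, with added noise and possible bias if the curve is misspecified or dropout is informative. At most the planned 40% of randomized pairs could be affected, and fewer if some losses come before birth. No inflation of type I error is shown for values taken from an infant's own curve. Severity is minor, because growth is a secondary endpoint and the repair is simple.

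**What to change.** - Replace the imputation sentence with a linear mixed model for each of weight, length and head circumference, fitted to the observed measurements. Include exact age at measurement, sex, group and group-by-age, and let the mean curve bend with age.
- Report group differences at the measured ages of 1, 2, 3, 6, 9 and 18 months, so that the analysis matches Objective V. Exact age in the model deals with the visit windows without a separate alignment step.
- Delete the 4-month estimate, or label it as interpolated and not measured.
- If curve-derived values are kept for any purpose, name the method and limit it to the age range in which that infant was measured.

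Infants with partial follow-up then contribute what was measured. The model still assumes that dropout is explained by the observed data, so it reduces the problem of informative loss but does not remove it. The cost is analysis wording and one model per measure, three in all, with no added visit or measurement.
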